Observational study of the correlation between peripheral Treg cell senescence and serum total cholesterol level

Version: 1.0

Date: December 1st, 2022

Ethics Committee

Tianjin Medical University General hospital

Protocol Abstract

Title	Observational study of the correlation between peripheral Treg cell senescence and serum total cholesterol level
Ethics Committee (Grant Number)	The ethics committee of Tianjin Medical University General Hospital (IRB2022-YX-244-01)
Principal Investigator	[name] (Ph.D.)
Sponsor	Tianjin Medical University General Hospital
Fundings	Natural Science Foundation of China (Grant No. 82071394, 82072166)
Execute Time	12/01/2022-03/31/2023
Recruiting Time	01/01/2023-03/31/2023
Objective	Clarify the correlation between human peripheral Treg cell senescence and serum total cholesterol level
Study Type	Observational
Time Perspective	Cross-Sectional
Enrollment	200 participants
Biospecimen	Description: Whole blood and serum Retention: Samples with DNA
Sampling Method	Probability sample
Condition	Hypercholesterolemia
Inclusion Criteria	1) Age \geq 30 and \leq 60 years old with independent behavior ability. 2) The participants need to fully understand the purpose and content of the study, and voluntarily participate in the study and sign the informed consent.
Exclusion Criteria	1) Pregnant or lactating women. 2) Acute and severe diseases in the last 3 months, including but not limited to, acute myocardial infarction, acute cerebral infarction, cerebral hemorrhage, circulatory failure, respiratory failure (internal diseases), trauma requiring hospitalization, or undergoes surgery under general anesthesia (surgical diseases).

	
3) History of severe diseases, including but not limited to, tumors, serious hematological diseases, serious cardiopulmonary diseases (interventional therapy for coronary artery disease, atrial fibrillation, chronic obstructive pulmonary disease, etc.), renal failure, liver failure, old stroke with serious sequelae.
 
4) Have participated in clinical trials in the past 3 months.
 
5) The investigator considers that not appropriate for inclusion.

Outcome Measures	Treg cell senescence evaluated by the beta-galactosidase (SA-betagal) activity test.
Reference standard	Protocols to detect senescence-associated beta-galactosidase (SA-betagal) activity, a biomarker of senescent cells in culture and in vivo. Nat Protoc 4, 1798-1806, doi:10.1038/nprot.2009.191 (2009)

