3.2 Exclusion Criteria

- 1) Pregnant or lactating women.
- 2) Acute and severe diseases in the last 3 months, including but not limited to, acute myocardial infarction, acute cerebral infarction, cerebral hemorrhage, circulatory failure, respiratory failure (internal diseases), trauma requiring hospitalization, or undergoes surgery under general anesthesia (surgical diseases).
- 3) History of severe diseases, including but not limited to, tumors, serious hematological diseases, serious cardiopulmonary diseases (interventional therapy for coronary artery disease, atrial fibrillation, chronic obstructive pulmonary disease, etc.), renal failure, liver failure, old stroke with serious sequelae.
- 4) Have participated in clinical trials in the past 3 months.

5) The investigator considers that not appropriate for inclusion.

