3.3 Withdrawal criteria

1) The subject decides to withdraw from the study.

2) The doctor or the researcher asks the subject to withdraw from the study (e.g. poor compliance).

4. Study procedure

Researchers initiate the study according to the inclusion/exclusion criteria. After confirming the subject has signed the informed consent, doctors will record the past medical history and medication (especially hypolipidemic drugs) in the past 3 months. Thereafter, an additional 6 ml of venous blood will be drawn during the routine blood tests for examinations of Treg cell senescence.

5. Evaluation Parameters

Treg cell senescence will be evaluated by the beta-galactosidase (SA-betagal) activity test.

6. Withdrawal of the subject

The subject has the right to withdraw from this trial at any time for any reason. The researcher should have a thorough understanding and a record of the reasons for withdrawal. Doctors and researchers also have the right to stop the subject from continuing to participate in the trial at any time during the research. Besides, subjects with early withdrawal should not be replaced by others.

As too many subjects withdrawing from the trial will lead to unreliable results, unnecessary withdrawal should be avoided. The falling rate of the trial should be controlled within 20%.

7. Statistical analysis

1. Pearson correlation coefficient was used to evaluate the correlation between the number of Treg cells in peripheral blood and serum total cholesterol level.

2. Taking the serum total cholesterol level of 5.17 mmol/L as the cut-off value, the subjects were divided into normal cholesterol level group and hypercholesterolemia group. Subsequently, the Propensity Score Matching (PSM) method was used to match the subjects according to gender, age and past medical history, and the Student's t-test was performed to compare the difference of Treg cell senescence between the two groups.

3. The serum total cholesterol level was stratified (e.g., trisection or quartering), and the difference of Treg cell senescence among all groups was compared using one-way ANOVA followed by LSD post-hoc test.

8. Trial Management

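### The matched comparison in section 7 item 2 leaves out hypolipidemic drug use, which section 4 records and which bears on the value that assigns the group; the size and direction of any bias are unknown

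*Protocol*

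**What the plan says.** The Protocol Abstract gives the objective as "Clarify the correlation between human peripheral Treg cell senescence and serum total cholesterol level". The exposure is therefore current serum total cholesterol.

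Section 4 (Study procedure) states that "doctors will record the past medical history and medication (especially hypolipidemic drugs) in the past 3 months". History and medication are two items there, and this drug class is singled out.

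Section 7 item 2 forms the groups: "Taking the serum total cholesterol level of 5.17 mmol/L as the cut-off value, the subjects were divided into normal cholesterol level group and hypercholesterolemia group". It then names the matching variables: the "Propensity Score Matching (PSM) method was used to match the subjects according to gender, age and past medical history". A Student's t-test without covariates follows.

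The inclusion criteria in section 3.1 do not mention medication. Section 3.2 lists conditions ("History of severe diseases, including but not limited to, tumors, serious hematological diseases, serious cardiopulmonary diseases" and others), recent trial participation and investigator judgement. Only the last could remove some drug users. No item of section 7 uses the medication data.

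**The concern.** Item 2 is not silent on covariates. It gives a closed list, and the list omits the one drug class that section 4 asks doctors to record with particular care. An analysis plan that added the variable would change a stated choice rather than fill a gap.

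The omitted variable is tied to the grouping: a drug that lowers total cholesterol can move a subject from one side of 5.17 mmol/L to the other. Matching on gender, age and history does nothing direct to balance it. The protocol hopes to build therapeutic strategies on the link between cholesterol and senescence, so a difference caused by treatment, or by what treated people have in common, would be read as a cholesterol effect. A real difference could equally be hidden.

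**Working it through.** **Reading.** Past medical history cannot be taken to include drug use, because section 4 names the two side by side. The omission is therefore in the text. The protocol states no figure for this point that could be reproduced.

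**Inputs for an illustration.** From the protocol: n = 200, cut-off 5.17 mmol/L, two-sided alpha 0.05. Assumed, not in the documents: all 200 analysed; untreated cholesterol N(5.0, 0.95) mmol/L; 10/20/30% of those above the cut-off treated; 25% reduction; no effect of cholesterol on senescence; the drug lowers senescence by 0.5 SD; residual SD 1.

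**Steps.**
- Share above the cut-off untreated: P(Z > (5.17 − 5.0)/0.95) = 0.429, or 85.8 of 200. Users: 8.6/17.2/25.7.
- A user stays above the cut-off only if the untreated value exceeds 5.17/0.75 = 6.89. P = 0.0231.
- Spurious difference (high minus normal) = 0.5 × (user share in normal group − user share in high group).

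The answer depends on who is treated. Before matching:

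| Treatment pattern (assumed) | Users still above 5.17 | User share, normal group | User share, high group | Difference, SD |
|---|---|---|---|---|
| Flat: same chance for all above 5.17 | 5.4% | 6.6/12.4/17.6% | 0.6/1.3/2.3% | 0.03/0.06/0.08 |
| Graded: chance rises with the excess over 5.17 | about 16% | 5.9/11.2/16.0% | 1.7/3.8/6.3% | 0.02/0.04/0.05 |
| Only the top 10% of those above 5.17 | 54% | 3.3% | 5.7% | −0.01 |

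Example, flat rule at 10%: 0.0231/0.429 = 5.4% of users stay above, so about 8.1 of 8.6 are below. The normal group has 114.2 + 8.1 = 122.3 members, and 8.1/122.3 = 6.6%. The high group has 77.7, of whom 0.46 (0.6%) are users. The difference is 0.5 × (0.066 − 0.006) = 0.03 SD.

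**Does the planned matching help?** Simulation under the flat rule: 10,000 replicates; age uniform 30-60; gender 50/50; binary age-related history; 1:1 nearest-neighbour matching with a caliper of 0.2 SD of the logit score. Matching leaves the user share of the normal group at 6.7/12.4/17.6%. The spurious difference is 0.027/0.055/0.078 SD and the t-test's type I error 5.4/6.2/6.8%. With a 1 SD drug effect these are 0.057/0.110/0.154 SD and 6.2/9.6/12.2%. If history includes a lipid diagnosis that marks 80% of users, the user share rises to 8.7/14.9/19.0% and the difference for 0.5 SD to 0.038/0.068/0.085 SD.

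**Does the remedy help?** With exact matching on drug use the difference is about 0 and type I error 4.6-5.3%. This requires that treatment is unrelated to other causes of senescence. With an unmeasured cause (0.5 SD on senescence, correlation 0.7 with treatment propensity) and no drug effect, the difference is −0.105/−0.176/−0.234 SD as written, −0.068/−0.122/−0.172 after exact matching and −0.068/−0.123/−0.176 in non-users. If a 1 SD drug effect is added, the two biases partly cancel as written (−0.045/−0.065/−0.081), so the adjusted estimate can lie further from zero.

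**The case against.** A reader might infer that users necessarily gather in the normal group. The documents do not support that. They give no share of users and no cholesterol distribution, and the table shows the imbalance shrinking under graded treatment and reversing when only the highest values are treated. This objection stands, and the direction must be left open.

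A reader might also infer that treated subjects are misclassified. They are not: the objective concerns current cholesterol, and they are grouped correctly on it. Nor does the argument reach item 1, which examines the "correlation between the number of Treg cells in peripheral blood and serum total cholesterol level", that is, cell number and not senescence.

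The strongest case for the plan is causal. If the drug acts on senescence only through cholesterol, and treatment is unrelated to other causes of senescence, drug use does not confound the comparison and leaving it out is defensible. That is correct, but the protocol does not argue it, and the unadjusted analysis cannot test it.

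It can also be said that the harm is small and the remedy imperfect. Both hold: type I error stays at or below 6.8% in the age-related-history simulation for a 0.5 SD drug effect, and adjustment does not remove bias from unmeasured causes. The age cap of 60 and the exclusions may also keep users few. This limits the priority of the point but does not remove it.

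A case for exact matching on the ground that the high group will often contain no user depends on the treatment pattern as well. Under the flat rule that happens in 62/39/25% of samples, under the graded rule in about 25/6/2%. Exact matching is therefore a fallback and not a necessity.

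**Conclusion.** The point holds in a limited form. Item 2 fixes a matching set that leaves a recorded variable, tied to the grouping value, unbalanced. The comparison is open to confounding if drug use affects senescence other than through cholesterol or marks other causes of senescence; if neither is so, there is no bias. Size and direction cannot be derived from the documents. With 10-30% of those above the cut-off treated and a 0.5 SD drug effect, the flat and graded patterns give about 0.02-0.08 SD, marginally more if history includes a lipid diagnosis. The sign can change if only the highest values are treated. Matching was simulated only under the flat pattern; the other rows are arithmetic before matching. This is an improvement worth considering, not a defect that invalidates the analysis.

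**What to change.** In section 7 item 2, add hypolipidemic drug use in the past 3 months (yes/no) to the matching variables and report its balance after matching. If too few users lie above the cut-off for a propensity term to be estimated, match on it exactly. Repeat item 2 in non-users as a sensitivity analysis. Item 3, where "the difference of Treg cell senescence among all groups was compared using one-way ANOVA followed by LSD post-hoc test", may be repeated in the same way, but it is not part of the defect.

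The variable is already collected, so the cost is analytic. In the flat-rule illustration, exact matching takes the pairs from 74.5/68.0/60.6 to 73.5/66.9/59.7, about one pair, or 4-5 pairs if history includes a lipid diagnosis. The non-user analysis has about 191/183/174 subjects and 73/66/58 pairs.

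The protocol should state the limits:
- Some pairs or users are lost, and the non-user sample is smaller.
- When few users are above the cut-off, exact matching and restriction give similar answers, so agreement between them is weak reassurance.
- Neither removes bias if treatment is related to unmeasured causes of senescence.
- Where that bias and a drug effect partly cancel, the adjusted estimate can lie further from zero than the unadjusted one.

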Statistical Analysis	All statistical analyses were performed using SPSS Statistics Version 27.0 (IBM, Armonk, NY, USA). A two-tailed p value of less than 0.05 was considered to be statistically significant.

1. Research Background and Objectives

Hypercholesterolemia is a risk factor for the occurrence and development of atherosclerosis. Recent animal studies have found that increased serum cholesterol level is associated with peripheral Treg cell senescence, but clinical evidence is still lacking. The purpose of this study is to analyze the correlation between human peripheral Treg cell senescence and serum total cholesterol level using clinical blood samples, thus laying a foundation for the establishment of novel therapeutic strategies for atherosclerosis based on the regulation of Treg cell senescence.

2. Study design

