2.2 Estimated number of subjects

Estimated by statistical analysis, a total of 200 subjects were randomly selected from the population receiving physical examination in the Cadre Physical examination Center of Tianjin Medical University General Hospital from January 2023 to March 2023.

3. Inclusion, Exclusion and Withdrawal Criteria

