3.1 Inclusion Criteria

- 1) Age ≥ 30 and ≤ 60 years old with independent behavior ability.
- 2) The participants need to fully understand the purpose and content of the study, and voluntarily participate in the study and sign the informed consent.

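### Section 7 item 2, the only confounder-controlled analysis, compares the propensity-matched groups with a plain Student's t-test that makes no adjustment for the matching covariates

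*Protocol*

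**What the plan says.** Protocol section 7 lists three analyses. Item 2 forms two groups, "Taking the serum total cholesterol level of 5.17 mmol/L as the cut-off value". It then states that the "Propensity Score Matching (PSM) method was used to match the subjects according to gender, age and past medical history", and finally that "the Student's t-test was performed to compare the difference of Treg cell senescence between the two groups".

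The text does not call the t-test independent or paired, gives no matching ratio, and mentions no covariates at the comparison step.

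The other two items are unadjusted. Item 1 is a Pearson correlation, worded for the number of Treg cells. Item 3 is a one-way ANOVA across cholesterol strata with LSD comparisons. Item 2 is therefore the only place where a confounder is controlled.

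The sample behind it is one draw: "a total of 200 subjects were randomly selected from the population receiving physical examination" (section 2.2). Section 3.1 admits ages 30 to 60. The abstract sets a two-sided 5% level.

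**The concern.** The outcome is a marker of cell senescence, and the protocol itself treats age as a variable to be matched. What the matching leaves unbalanced therefore matters, and so does how the matched data are tested. A plain t-test handles neither in full.

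- **Precision.** Matched subjects resemble each other on variables that may predict senescence, so their outcomes tend to be positively correlated. A two-sample test ignores this, and its standard error is too large.
- **Leftover imbalance.** A t-test has no covariates, so any age, gender or history difference that survives the matching goes straight into the group difference. Both groups come from one sample of 200 cut at a threshold. If the cut falls near the middle, there is no reserve of spare subjects to match from. One-to-one matching must then either drop subjects or keep nearly all of them and most of the original age gap.

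At stake is the one comparison in the study that could separate cholesterol from age.

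**Working it through.** The protocol gives no expected difference, standard deviation or power for item 2, so there is no figure to reproduce.

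**Inputs from the protocol.** N = 200 (section 2.2), or 0.80 × 200 = 160 at the 20% loss ceiling in section 6; two-sided 5% (abstract); ages 30-60 (section 3.1); matching on gender, age and history (section 7).

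**Assumptions (not in the protocol).** Correlation of age with cholesterol 0.3; of age with senescence 0.3 or 0.5; 30%, 40% or 50% of subjects above 5.17 mmol/L; logistic propensity score; greedy 1:1 nearest-neighbour matching without replacement, with no caliper or a caliper of 0.2 SD of the logit.

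**Step 1: precision.** With within-pair outcome correlation ρ, the two-sample standard error exceeds the paired one by the factor 1/√(1−ρ), and the actual type I error is 2 × [1 − Φ(1.96/√(1−ρ))].

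| ρ | SE factor | Type I error |
|---|---|---|
| 0.08 | 1.04 | 4.1% |
| 0.16 | 1.09 | 3.3% |
| 0.24 | 1.15 | 2.5% |

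The simulated ρ was 0.05-0.07 when age correlates 0.3 with senescence and 0.14-0.19 when it correlates 0.5. The standard error is then about 3-4% and 8-12% too wide. For example, 0.163/0.146 = 1.12 at 50% above the cut-off with a caliper.

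In a second set of simulations the covariates explained 10-30% of senescence variance and a 0.2 SD caliper was used. The excess was 4-15%, and power for a 0.4 SD difference fell by 1-10 points (at 30% explained, 0.63 against 0.71 and 0.71 against 0.81).

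**Step 2: leftover imbalance.** No true effect, N = 200, age-senescence correlation 0.5, 600 runs per row. Adjusted means regression on group, age, gender and history in the matched set, here with ordinary standard errors.

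| Above cut-off | Caliper | Pairs | Age gap before → after (SD) | Two-sample t rejects | Paired t rejects | Adjusted rejects |
|---|---|---|---|---|---|---|
| 30% | none | 60 | 0.50 → 0.02 | 4.0% | 6.3% | 6.0% |
| 30% | 0.2 | 57 | 0.51 → 0.00 | 2.8% | 4.5% | 5.5% |
| 40% | none | 80 | 0.48 → 0.14 | 5.7% | 8.8% | 4.7% |
| 40% | 0.2 | 69 | 0.49 → 0.00 | 2.7% | 4.8% | 4.7% |
| 50% | none | 94 | 0.49 → 0.36 | 25.0% | 29.3% | 5.5% |
| 50% | 0.2 | 74 | 0.50 → 0.00 | 2.2% | 3.0% | 4.2% |

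Monte Carlo error is about 1-2 percentage points. In the fifth row 2 × 94 = 188 of 200 subjects are kept, so the matched set is nearly the whole sample.

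**Step 3: check of the fifth row by hand.** The leftover bias is 0.191 SD, the two-sample SE 0.144 and the actual spread of the estimate 0.146. The rejection limit is 1.96 × 0.144 = 0.282, and (0.282 − 0.191)/0.146 = 0.62, which gives about 27%, in line with 25.0%. The paired SE is 0.133: the limit is 0.261, (0.261 − 0.191)/0.146 = 0.48, which gives about 32%, in line with 29.3%. Pairing leaves the bias unchanged and shrinks the error bar.

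**Step 4: sensitivity.** In the fifth-row setting, N = 160 gives 21.3% for the two-sample test, and an age-senescence correlation of 0.3 (N = 200) gives 9.7%. The second set of simulations, without a caliper and near 50:50, gave 13%, 19% and 28% for 10%, 20% and 30% of variance explained. It gave 14% at 45:55 (20% explained) and 3-5% at 35:65. The paired test without a caliper rejected 15-34%. Regression with pair-clustered standard errors held 5-6%.

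**The case against.** The best defence has four parts.

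- **The protocol never says independent-samples, and never says pairs.** This is correct. A reader might infer that it prescribes a test that ignores pairing; it supports only that the form is unstated and the two-sample test is the natural reading. The leftover-imbalance point does not depend on this, because a paired t-test carries the same bias.
- **The precision fault is small and on the safe side.** This also stands. With a caliper the two-sample test rejected 1.8-4.5% of the time under the null, and whether propensity-matched samples must be analysed as pairs is disputed. The cost is some power, not false claims.
- **Leftover age imbalance comes from the matching, not from the t-test.** This is largely right: a 0.2 SD caliper left 0-1% of the age gap at every split, with the t-test unchanged. Caliper, ratio and balance checks are commonly left to a statistical analysis plan, so their absence here is not a fault. What remains is that the test the protocol does fix cannot correct whatever the matching leaves, whereas an adjusted comparison can, whichever matching rule is used.
- **The large error rates need two conditions that the protocol does not state:** no caliper, and groups of similar size. This stands as well. The share above 5.17 mmol/L is not given.

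**Conclusion.** The point holds in a limited form. The one analysis that controls confounding ends in an unadjusted t-test, and its behaviour depends on how the matching turns out.

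- **Tight matching:** mildly conservative, with a standard error roughly 3-15% too wide and up to about 10 points of power lost.
- **Loose matching with near-equal groups:** up to about three quarters of the age gap remains (0.36/0.49 = 73%), and false positives rise to about 10-28% for the two-sample test, with the paired test no better.
- **Clearly unequal groups, or a caliper:** this bias is small.

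A reader might infer that the comparison will produce a false-positive result. The documents do not support that: it takes both no caliper and a near-even split, and the protocol states neither. All covariate strengths and group splits above are assumptions, so the figures show a plausible range, not a forecast. The change is worth making because it is cheap and makes the comparison less dependent on the matching details.

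**What to change.** In section 7 item 2, replace the t-test sentence with wording such as: *In the matched set, the difference in Treg cell senescence between cholesterol groups is estimated by linear regression on group, with gender, age and past medical history as covariates and standard errors clustered on matched set; the adjusted difference and its 95% CI are reported.*

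Naming a paired t-test instead would address only the precision point.

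The change costs one sentence. Medical history is recorded under section 4, and gender and age under section 8.2, so no data or subjects are added. The only consequence is that the result is an adjusted rather than a raw difference.

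### Section 7, item 3 tests Treg senescence across cholesterol strata without the covariates that item 2 balances, so an age gradient can pass for a cholesterol gradient

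*Protocol*

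**What the plan says.** The Protocol Abstract gives the objective: "Clarify the correlation between human peripheral Treg cell senescence and serum total cholesterol level". Section 7 of the protocol then lists three analyses.

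- **Item 1** is a Pearson coefficient for the "correlation between the number of Treg cells in peripheral blood and serum total cholesterol level". It is unadjusted, and its outcome is cell number, not senescence.
- **Item 2** splits total cholesterol at 5.17 mmol/L, uses propensity scores to "match the subjects according to gender, age and past medical history", and compares senescence by t-test.
- **Item 3** divides total cholesterol into, for example, three or four strata, and "the difference of Treg cell senescence among all groups was compared using one-way ANOVA", followed by LSD comparisons.

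No item is named primary, and none is called crude or adjusted. Item 3 does not say whether it uses all subjects or only the matched ones. Section 3.1 sets the age range: "Age ≥ 30 and ≤ 60 years old with independent behavior ability".

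**The concern.** Items 2 and 3 ask about the same exposure and the same outcome. By matching, item 2 treats gender, age and medical history as variables that can distort the comparison. Item 3 ignores them, because one-way ANOVA and LSD take no covariates.

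Item 3 is also the only analysis that can show a graded relation of senescence to cholesterol, since item 1 uses another outcome and item 2 has only two groups. If older subjects have both higher cholesterol and more senescent cells, the strata differ in age and therefore in senescence, even if cholesterol plays no part. Every pairwise LSD contrast inherits the same distortion. A reader could separate the two explanations only by setting item 3 against item 2, which cannot show a gradient.

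**Working it through.** **Inputs from the protocol.** There are 200 subjects (Section 2.2), a two-sided 0.05 level (Protocol Abstract), and three or four strata (Section 7, item 3). Section 6 says "The falling rate of the trial should be controlled within 20" per cent and that "subjects with early withdrawal should not be replaced by others", so the permitted loss leaves 200 × 0.80 = 160. The 200 cannot be reproduced, because no effect size, SD or power is given. The point does not depend on it.

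**Assumptions.** The protocol gives neither the age–cholesterol correlation (*a*) nor the age–senescence correlation (*b*), so a range is shown. Age is uniform on 30–60 and standardised to *z*. Cholesterol = *a·z* + √(1−*a*²)·*e*₁ and senescence = *b·z* + √(1−*b*²)·*e*₂, with independent errors and **no cholesterol effect**. Half the subjects are of each gender, 30% have a medical history, and neither affects the outcome.

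**Induced association.** Age alone produces a cholesterol–senescence correlation of *a·b*. For roughly normal cholesterol, the mean difference between outer strata is about 2.18 SD for tertiles (2 × 1.09) and 2.54 SD for quartiles (2 × 1.27). The spurious senescence gap is therefore about *a·b* × 2.18 to *a·b* × 2.54. With *a* = 0.3 and *b* = 0.4, that is 0.12 × 2.18 = 0.26 to 0.12 × 2.54 = 0.30 SD; the simulation gave 0.27–0.31.

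**Test.** With *k* strata, the crude test is F = [(RSS₀ − RSS₁)/(k−1)] / [RSS₁/(n−k)]. The adjusted test adds age, gender and history to both models and uses n−k−3 error degrees of freedom.

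**Significant results from the crude ANOVA with no cholesterol effect** (8,000 runs per setting, tertiles / quartiles):

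| *a*, *b* | *a·b* | N = 200 | N = 160 | Spurious outer gap (SD), N = 200 |
|---|---|---|---|---|
| 0.1, 0.2 | 0.02 | 5.3 / 5.5% | 5.4 / 5.4% | 0.04–0.05 |
| 0.2, 0.3 | 0.06 | 9.9 / 9.3% | 8.3 / 8.3% | 0.13–0.15 |
| 0.2, 0.5 | 0.10 | 18.7 / 17.6% | 15.0 / 13.9% | 0.22–0.25 |
| 0.3, 0.4 | 0.12 | 26.0 / 23.8% | 21.3 / 19.0% | 0.27–0.31 |
| 0.3, 0.5 | 0.15 | 39.4 / 36.1% | not run | 0.33–0.38 |

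The adjusted test gave 4.7–5.6% at N = 200 and 4.4–5.4% at N = 160. Its outer-stratum gap at N = 200 was 0.00 SD. The simulation standard error at 5% is √(0.05 × 0.95/8000) = 0.24 percentage points.

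A variant with normally distributed age and age as the only covariate (4,000 runs) gave, at N = 200, crude rates of 24.0 / 22.2% for 0.3, 0.4 and 37.7 / 35.2% for 0.3, 0.5. At N = 160 the latter pair gave 30.0 / 28.6%. With both correlations zero at N = 200, the crude rate was 5.1 / 5.0%, as it should be.

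**Power of the adjusted test.** With a true effect of 0.2 SD per SD of cholesterol (5,000 runs), analysis of covariance has 58–67% power at N = 200 and 47–57% at N = 160. Where age is unrelated to cholesterol (0, 0.4), so that the crude test is unbiased, power at N = 200 is 66 / 64% adjusted against 59 / 57% crude.

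**The case against.** - **The objective is a correlation in a cross-sectional study, and a crude association answers it.** This stands in part. If the target is the marginal association, *a·b* is real and the percentages above are not error rates. But item 2 pursues the same objective with matching, and nothing tells the reader that item 3 has a different target.
- **Labels and supplementary models belong in an analysis plan that is not shown.** This does not defeat the point. The protocol itself fixes the method for item 3, and that method conflicts with its treatment of the same question in item 2.
- **Item 2 already supplies a balanced comparison.** This mitigates the problem, but two groups cannot show a gradient.
- **Item 3 may be meant for the matched set.** The text leaves this open, though a fresh stratification compared among all groups reads more naturally as all subjects. In a check with 1:1 age matching at N = 200 (3,000 runs, pairs 0.3, 0.4 and 0.4, 0.5), the false-positive rate fell to 4.5–5.4% for tertiles and 5.3–8.9% for quartiles. Age gaps of 0.14–0.29 SD between outer strata remained. Most of the bias would go, but not all of it for quartiles.
- **The figures are assumed, and the model favours adjustment.** This stands. The age effect is linear and correctly modelled, and gender and history have no effect, so the figures say nothing about confounding by those two.
- **Adjustment can cost power.** At 0.1, 0.2 with tertiles and N = 200, crude power is 67% against 60% adjusted. At least part of that difference is the age-induced association itself.
- **Medical history is not defined, and some conditions may follow from high cholesterol.** This is a fair caution, but item 2 must already code that variable in order to match on it.

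**Conclusion.** The concern holds. For the same exposure and outcome, the protocol balances three variables in item 2 and ignores them in item 3, without calling item 3 crude or pairing it with an adjusted result. The size for this study is unknown. It is negligible if age is weakly related to both variables (5–6% significant at 0.1 and 0.2) and serious at 0.3 and 0.4 or above (24–26%, rising to 36–39% at 0.3 and 0.5, with 200 subjects). These rates assume that the target is a cholesterol relation not explained by age, that all subjects are analysed, and that the assumed correlations apply. They should not be read as this study's error rate. The point should be fixed, but it does not undermine the whole plan, because item 2 gives a partial guard. The figures do not apply to item 1, whose outcome is cell number.

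**What to change.** - **Item 3:** replace one-way ANOVA with analysis of covariance on item 2's covariates (gender, age, medical history), with pairwise comparisons of adjusted means. Keep the one-way ANOVA as a result labelled crude and descriptive. State whether all subjects or only the matched ones are analysed, and list the conditions that make up medical history, coded the same way as for item 2.
- **Item 1:** for the outcome it names, report a partial correlation or linear regression with the same covariates, and label the plain Pearson coefficient crude. That item 1 studies cell number while the objective concerns senescence is a separate matter, which this change does not settle.
- **Optional sensitivity analysis:** add lipid-lowering drug use as a covariate.

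The cost is protocol wording, plus the coding of medical history that item 2 already requires. Section 8.2 collects gender and age, and under Section 4 "doctors will record the past medical history and medication (especially hypolipidemic drugs) in the past 3 months". SPSS, which the protocol names, runs these models. No further subjects, blood samples or assays are needed.
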